5.5.4. Death

Any death of a research subject that is possibly, probably or definitely related to the research must be reported within 24 hours of an investigator becoming aware of the death.

5.5.5. New Information

New information that might affect the willingness of a subject to enroll or remain in the study should be reported within 7 calendar days of an investigator first becoming aware.

5.5.6. Suspension or Termination of Research Activities

Any suspension or termination of research activities, including holds on new enrollment, placed upon the research by the study sponsor, NIH or IC leadership, or any regulatory agency must be reported within 7 calendar days of an investigator becoming aware.

5.5.7. Expedited Reporting to the IRB

Death related to research must be reported within **24 hours**.

The following will be reported within **7 calendar days** of investigator awareness:

- Actual or suspected UPs;
- Actual or suspected non-compliance;
- Actual or suspected Major PDs;
- SAEs that are actual or suspected UPs;
- New information that might affect the willingness of a subject to enroll or remain in the study;

Suspension or termination of research activities, including holds on new enrollment, placed upon the research by the study sponsor, NIH or IC leadership, or any regulatory agency.

5.5.8. Annual Reporting to the IRB

The following will be reported to the IRB in summary at the time of Continuing Review:

- Summary of UPs and non-compliance;
- AEs, including SAEs, that are not UPs, as a narrative summary statement indicating whether these events were within the expected range;
- Minor PDs (aggregate summary);
- Any trends or events which in the opinion of the investigator should be reported.

5.6. Reporting of Pregnancy

Pregnancy is not an adverse event, but pregnancy, if it occurs during the time of study participation, will be recorded in the study database, and notification on the pregnancy will be distributed to the study team and to the IND Sponsor. Subjects will be followed for clinical safety and to collect the pregnancy outcome as described in [Section 4.2.1](#). Congenital abnormalities or birth defects and spontaneous miscarriages that meet serious criteria ([Section Error! Reference source not found.](#)) will be reported as SAEs. Pregnancy outcome will be reported to the IND Sponsor and to regulatory agencies.

6. STATISTICAL CONSIDERATIONS

6.1. Overview

This is a phase I, open-label, dose-escalation study in healthy adults to assess the safety, tolerability, dose, and PK of VRC01.23LS (VRC-HIVMAB0115-00-AB), a human monoclonal antibody with broad HIV-1 neutralizing activity.

6.2. Accrual and Sample Size Considerations

Recruitment will target about 22 healthy adults, 18 to 60 years of age, with 3 subjects in each of the single dose groups (Groups 1 through 4) and 5 subjects in the repeat dose groups (Groups 5 and 6) as shown in [Table 2](#). The permitted accrual is 40 subjects in total to allow for additional enrollments in the event that an enrolled subject does not complete the minimum evaluations needed to meet the protocol criteria for the group dose safety or dose-escalation evaluation. Dose escalation rules are described in [4.4](#).

6.2.1. Group Assignments

The Advantage eClinical system (The Emmes Company LLC, Rockville, MD) will be used to assign subjects to a dose group in active accrual at the time of enrollment. If an enrolled subject discontinues from the study before he/she has received study product, a new eligible subject may be enrolled into the same group. If a replacement subject is needed in the case of a subject withdrawal, the replacement subject will be assigned to the same group as the dropout subject.

6.2.2. Sample Size Considerations

The goal of the safety evaluation is to identify safety concerns associated with product administration. The ability of the study to detect SAEs can be expressed by the true event rate above which at least 1 SAE would likely be observed and the true event rate below which no events would likely be observed. For this study, group sizes are targeted to be n=3 or n=5, and within this section, an event is defined as a subject experiencing at least one event.

For n=3, there is at least a 90% chance of observing at least 1 event if the true rate is 0.536 or more and at least a 90% chance of observing no events if the true rate is 0.035 or less. For n=5, there is at least a 90% chance of observing at least 1 event if the true rate is 0.369 or more and at least a 90% chance of observing no events if the true rate is 0.021 or less.

Probabilities of observing 0, 1 or more, and 2 or more events among group sizes n=3 and n=5 are presented in [Table 4](#) for a range of possible true event rates. These calculations provide a more complete picture of the sensitivity of this study design to identify potential safety problems with product administration.

Table 4: Probability of Observing a Given Number of Events for Different True Event Rates

True event rate	N=3			N=5		
	Pr (0 events)	Pr (1+ events)	Pr (2+ events)	Pr (0 events)	Pr (1+ events)	Pr (2+ events)
0.01	0.970	0.030	<0.001	0.951	0.049	0.001
0.05	0.857	0.143	0.007	0.774	0.226	0.023
0.10	0.729	0.271	0.028	0.590	0.410	0.081
0.20	0.512	0.488	0.104	0.328	0.672	0.263
0.30	0.343	0.657	0.216	0.168	0.832	0.472
0.40	0.216	0.784	0.352	0.078	0.922	0.663

Table 5 displays the two-sided 95% confidence intervals (CIs) for the probability of an event based on observed events for n=3 and n=5 using the exact method. For example, if none of the subjects experience a particular safety event, the 95% two-sided upper confidence bound for the true rate of such events in the population is 0.708 for n=3 and 0.522 for n=5.

Table 5: Two-sided 95% Confidence Intervals for Probability of an Event Based on Observed Event Rate

Observed event rate	95% CI for N=3	Observed event rate	95% CI for N=5
0/3	0.000, 0.708	0/5	0.000, 0.522
1/3	0.008, 0.906	1/5	0.005, 0.716
2/3	0.094, 0.992	2/5	0.053, 0.853
3/3	0.292, 1.000	3/5	0.147, 0.947
-	-	4/5	0.284, 0.995
-	-	5/5	0.478, 1.000

6.3. Statistical Analysis

6.3.1. Analysis Variables

The analysis variables will consist of baseline, pharmacokinetics, and safety variables to support analyses of the primary and secondary objectives. Continuous variables will be summarized using descriptive statistics, and categorical variables will be summarized using counts and percentages.

6.3.2. Baseline Characteristics

Descriptive statistics will be used to summarize baseline characteristics, inclusive of demographics and safety laboratory measurements.

6.3.3. Safety Analysis

Subjects who receive at least one administration will be considered in the safety analyses.

Solicited Adverse Events: Solicited AE data will be collected for 7 days after each product administration. When summarizing the number and percentage of subjects experiencing each

solicited sign or symptom, subjects with multiple occurrences of the same event will be counted once, and only the maximum severity level will be presented. Solicited AEs will be summarized by route and dose level for each administration.

Adverse Events: All reportable AEs will be recorded and coded by Medical Dictionary for Regulatory Activities (MedDRA) system organ class (SOC) and preferred term (PT). The number and percentage of subjects with each unsolicited AE will be summarized by group (Groups 1 through 6). Subjects with multiple occurrences of the same event will be counted once; only the maximum severity level will be presented in severity summaries, and the strongest relationship level will be presented in relationship summaries.

A by-subject listing of all unsolicited AEs will provide details including severity, relationship to treatment type, seriousness, new medical condition status, onset and end date, onset study day, duration, and outcome.

Local laboratory values: By-subject listings will present laboratory data measured during the course of the study and may include change from baseline values and reference ranges for abnormal findings.

Additional listings may be included, such as disposition and administration status, concomitant medications, protocol deviations, or vital signs.

6.3.4. Tolerability Evaluation

The tolerability of an investigational medicinal product represents the degree to which overt adverse effects can be tolerated by the subject [32]. Since VRC 615 is the first trial of VRC01.23LS in healthy adults, the tolerability evaluation will include mostly descriptive summaries of the frequency of solicited AE reports with an onset in the 3 days following each administration and subject withdrawals or discontinuations based upon subject discomfort or AEs. This early assessment of tolerability will inform the parameters to solicit or routinely assess in future studies to further characterize the tolerability profile in a larger subject cohort.

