3. STUDY OBJECTIVES

3.1. Primary Objectives

- To evaluate the safety and tolerability of VRC01.23LS in healthy adults when administered SC as a single dose at 5 mg/kg.
- To evaluate the safety and tolerability of VRC01.23LS in healthy adults when administered IV as a single dose at 5, 20, or 40 mg/kg.
- To evaluate the safety and tolerability of VRC01.23LS in healthy adults when administered by repeat SC dosing at 5 mg/kg, for a total of 3 injections in 12-week intervals.
- To evaluate the safety and tolerability of VRC01.23LS in healthy adults when administered by repeat IV dosing at 20 mg/kg, for a total of 3 infusions in 12-week intervals.

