5. SAFETY AND ADVERSE EVENTS

5.1. Adverse Events

An adverse event (AE) is any untoward medical occurrence associated with the use of a drug in humans, whether or not considered drug related.

- Solicited AEs (i.e., reactogenicity parameters as defined in [4.3.6](#)) will be recorded without attribution assessments by the subject on paper or electronic diary for 7 days after each product administration.
- Unsolicited AEs will be recorded in the study database with attribution assessments from product administration through the Day 28 post-product administration visit.
- SAEs (as detailed in [5.2](#)) and new chronic medical conditions will be recorded as AEs through the last expected study visit or contact.

[Appendix II](#) describes how the relationship between an AE and the study product will be assessed. Also available in [Appendix II](#) is the link to the DAIDS Table for Grading the Severity of Adult and Pediatric Adverse Events, Corrected Version 2.1 [July 2017], which will be used to determine the severity grades of AEs in this protocol with several modifications as noted.

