Delayed allergic reactions to other mAbs may include a serum sickness type of reaction, which is characterized by urticaria, fever, lymph node enlargement, and joint pains. These symptoms may not appear until several days after the exposure to the mAb and are noted to be more common with chimeric types of mAbs [41].

There are several FDA-licensed mAbs for which reactions related to the rate of IV infusion have been described. Some symptoms may be treated by slowing or stopping the infusion. Supportive treatment may also be indicated for some signs and symptoms.

Participation in this study may limit a subject’s eligibility for other future mAb studies.

Risks of Blood Drawing

Blood drawing may cause pain and bruising and may, infrequently, cause a feeling of lightheadedness or fainting. Rarely, it may cause infection at the site where the blood is taken. In this study, an IV line that can be used for the collection of blood may be left in place for several hours on the days when there are frequent PK blood draws. Problems from use of an IV for blood drawing are generally mild and may include pain, bruising, minor swelling or bleeding at the IV site and rarely, infection, vein irritation (called phlebitis), or blood clot.

Risks of IV Infusions or SC Injections

General risks of methods that use a needle include stinging, discomfort, pain, soreness, redness, bruising, swelling or a tiny cut at the needle insertion site.

Risks of New Diagnoses

It is possible that the standard medical tests performed as part of this research protocol will result in new diagnoses. Depending upon the medical findings and consequences of being provided with the new medical information about health status, the study subject may view this aspect of study participation as either a risk or a benefit. Any such information will be shared and discussed with the subject and, if requested by the subject, will be forwarded to the subject’s primary health care provider for further workup and management.

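### Does the 3-day onset window in the tolerability evaluation (Section 6.3.4) hide late reactions that the 7-day diary collects?

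*Combined protocol and SAP*

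**What the plan says.** Section 6.3.4 states that "the tolerability evaluation will include mostly descriptive summaries" of two things. The first is the "frequency of solicited AE reports with an onset in the 3 days following each administration". The second is "subject withdrawals or discontinuations based upon subject discomfort or AEs", which carries no time limit. The section gives no reason for 3 days and does not say whether Day 0 counts. It adds that this early assessment will inform what is solicited or routinely assessed in later studies.

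Section 6.3.3 covers the same diary data under safety: "Solicited AE data will be collected for 7 days after each product administration", and "Solicited AEs will be summarized by route and dose level for each administration". Each subject is counted once per symptom, at maximum severity. Section 5.1 sets the wider net: "Unsolicited AEs will be recorded in the study database with attribution assessments from product administration through the Day 28 post-product administration visit". Serious events and new chronic conditions are recorded through the last expected visit or contact.

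The four primary objectives in Section 3.1 share one form, for example "To evaluate the safety and tolerability of VRC01.23LS in healthy adults when administered SC as a single dose at 5 mg/kg". None of them names tolerability apart from safety.

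**The concern.** Tolerability appears in every primary objective, and Section 6.3.4 is the only place that says how it will be evaluated. Its solicited-event component stops at onset within 3 days, although Sections 4.3.6, 5.1 and 6.3.3 all give a 7-day diary. Section 8.2.1 describes serum-sickness-type reactions and says of them: "These symptoms may not appear until several days after the exposure to the mAb". Fever and joint pain belong to that picture and are diary items, so an onset on Days 4 to 7 would be collected and then left out of the tolerability summary.

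The omission can work in one direction only: a 3-day subset never shows more affected subjects than the 7-day data. If the plan had no other summary, the tolerability conclusion could look better than the data support, and the choice of parameters for later studies would lack the delayed events. A reader would also meet two solicited-event frequencies for the same subjects, with no text linking them.

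**Working it through.** **1. Inputs.** Group sizes are 3 (Groups 1 to 4) and 5 (Groups 5 and 6), from Table 2. Groups 5 and 6 receive three doses each. The diary runs 7 days (Sections 4.3.6 and 6.3.3) and the onset window is 3 days (Section 6.3.4). The documents give no distribution of onset times.

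**2. The plan's own figures.** Table 4 uses P(at least one event) = 1 − (1 − p)^n. At p = 0.20 this gives 1 − 0.8^3 = 0.488 and 1 − 0.8^5 = 0.672, as printed.

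**3. Collection time outside the window.** Administrations: 4 × 3 + 10 × 3 = 42. Diary days: 42 × 7 = 294. If the window means Days 1 to 3, then 42 × 4 = 168 days fall after it, and 168/294 = 57%. This is a share of calendar time, not of events. Section 8.2.1 says most infusion-related events occur within 24 hours, and Section 1.3.2 describes reactogenicity to the parent antibody as arising shortly after dosing. Both suggest that the share of events is smaller.

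**4. Effect on the Section 6.3.4 summary.** Let f be the share of affected subjects whose onset is only after Day 3 (an assumption). Then P(at least one counted) = 1 − (1 − p(1 − f))^n. With p = 0.20:

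| f | n = 3 | n = 5 |
|---|---|---|
| 0 | 0.488 | 0.672 |
| 0.10 | 0.449 | 0.629 |
| 0.25 | 0.386 | 0.556 |
| 0.50 | 0.271 | 0.410 |

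The first row is also what the 7-day summary in Section 6.3.3 gives whatever the value of f.

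**5. The extreme case.** With a true rate of 0.30 in 5 subjects and every onset after Day 3, at least one subject is affected with probability 1 − 0.7^5 = 0.832, and the 3-day count shows none. Section 8.2.1 calls immune reactions of this kind rare. At rates of 0.01 and 0.05, Table 4 gives 0.049 and 0.226 for n = 5.

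**6. Where a Day 5 fever or joint pain would appear.**

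- Solicited-event table, Section 6.3.3: yes, at maximum severity.
- Solicited part of Section 6.3.4: no.
- Withdrawal and discontinuation part of Section 6.3.4: yes, if it led to either.
- Dose-escalation review, Section 4.4: yes, for subjects under review, because the minimum data run from Day 0 through at least the Day 7 visit.
- Pause criteria, Section 4.7: these contain no 3-day cut.

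**7. What the window cannot affect.** Urticaria and lymph node enlargement, the other two features of the delayed reaction, are not diary items in Section 4.3.6. They would be recorded as unsolicited events. A reaction that starts after Day 7 lies outside the diary under either window. The cut is on onset, so an event that begins on Day 2 and lasts beyond Day 3 stays in.

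**The case for a change.** The best case for a change is that Section 6.3.4 is the plan's only definition of the tolerability evaluation, and that its window is unexplained and not fully defined. The reference attached to the definition of tolerability is, by its title, a paper on identifying a CD4-binding-site antibody, so it does not support the choice of 3 days. The section has a stated use in later studies, for which late onset is relevant. The remedy would be one number and one table row, with no new data.

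Much of this stands as description. The mismatch is real, no rationale is given, and the treatment of Day 0 is left open. What does not stand is the consequence. The section says what the evaluation will include, not that nothing else counts, and its discontinuation component has no time limit. Its role in later studies is to inform, and nothing stops those planning them from reading the 7-day table beside it. Two summaries with different stated windows under different headings do not contradict each other.

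**Conclusion.** No change follows. Onsets on about Days 4 to 7 are missing from one descriptive summary but not from the trial's reporting of safety and tolerability, because Section 6.3.3 already gives the full diary period by route, dose level and administration. In the illustration with n = 5 and a 7-day rate of 0.20, the chance that the 3-day summary counts an affected subject falls by between 0 (no late onset) and 0.672 − 0.410 = 0.262 (half of affected subjects late). The Section 6.3.3 summary loses nothing. No test, sample size, escalation review or pause criterion depends on the 3-day count.

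Extending the window to 7 days would make the solicited part of Section 6.3.4 largely a copy of the Section 6.3.3 table. An acute-phase summary beside a full-period table is a fair descriptive choice for a product whose infusion-related events are expected mostly within 24 hours. The missing day convention is a gap that analysts fill when they label the table.

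This rests on two assumptions: that the Section 6.3.3 table is produced from the whole 7-day diary, as the text indicates, and that the report presents it together with the Section 6.3.4 summary.

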6.3.5. Pharmacokinetics Analysis

Blood samples for PK evaluations will be collected at time points based on participant study groups defined in the Schedule of Evaluations ([Appendix I](#)).

Individual Subject Pharmacokinetic Analysis:

Population pharmacokinetic analyses will be performed on the VRC01.23LS pharmacokinetic data following product administration to determine compartmental PK parameters as previously described [37-39]. One, two and three compartment pharmacokinetic models will be considered. Based on prior pharmacokinetic studies of bnAbs, including VRC01LS, it is anticipated that a two-compartment model will adequately characterize the data. The population analysis will generate estimates for initial and final volumes of distribution (Vd_1 and Vd_2), inter-compartmental clearance (Q), CL and bioavailability (F). Given the small subject numbers, the population PK analysis will include only a limited covariate analysis to assess clinical factors as fixed effects associated with VRC01.23LS PK parameters. Specifically dose level, repeat dosing and allotype will be assessed as applicable. Final model selection will be based on changes in the objective function and graphically by goodness of fit plots. The final population model will be

assessed using bootstrap analysis and Monte Carlo simulations will be utilized to assess dosing strategies to archive target VRC01.23LS concentrations.

Population Pharmacokinetic Analyses:

Population pharmacokinetic analyses will be performed on the VRC01.23LS pharmacokinetic data following product administration to determine compartmental PK parameters as previously described [26, 37, 40]. One, two and three compartment pharmacokinetic models will be considered. Based on prior pharmacokinetic studies of bNAbs, including VRC01LS, it is anticipated that a two-compartment model will adequately characterize the data. The population analysis will generate estimates for initial and final volumes of distribution (Vd1 and Vd2), inter-compartmental clearance (Q), CL and bioavailability (F). Given the small subject numbers, the population PK analysis will include only a limited covariate analysis to assess clinical factors as fixed effects associated with VRC01.23LS PK parameters. Specifically dose level, repeat dosing and allotype will be assessed as applicable. Final model selection will be based on changes in the objective function and graphically by goodness of fit plots. The final population model will be assessed using bootstrap analysis and Monte Carlo simulations will be utilized to assess dosing strategies to archive target VRC01.23LS concentrations

6.3.6. Interim Analyses

Preliminary PK analyses may be done as the data for each dose level is obtained. This may be performed before a dose group's PK data is complete and may only generate a subset of the final PK parameters. The interim analyses may be used to inform decisions about the dose levels to be administered in future studies.

6.3.7. Missing Data

Missing data will be assumed to be missing completely at random. Analyses will include all samples available at each study time point. Based on experience from previous trials, we expect missing data to be rare. Regardless, in the event of missing data, we will report the occurrence and extent of missingness. We will also provide plausible explanations for the missingness mechanism, should such information be available.

7. PHARMACY PROCEDURES

The dose groups and VRC01.23LS dosing schedule are shown in **Table 1**.

7.1. Study Product

VRC01.23LS (VRC-HIVMAB0115-00-AB) is a clear, colorless to yellow liquid, sterile aqueous buffered solution that is essentially free of visible particles (some opaque or translucent particles may be present) and is filled into 10 mL single-dose vials. Each vial contains a 6.25 ± 0.1 mL volume of VRC01.23LS at a concentration of 100 ± 10 mg/mL in formulation buffer composed of 20 mM Acetate Phosphate, 25 mM NaCl, 150 mM Arginine HCl, 5% Sucrose, 0.2% Polysorbate 80, pH 5.8.

